4.2 Inclusion criteria for enrolment

All participants must satisfy ALL the following criteria at study entry:

- Male and female adults ≥60 years of age (comorbidity, including chronic heart disease is not an exclusion criterion)
- Willing and able to give written informed consent
- Willing and able to adhere to protocol-specified procedures

4.3 Exclusion criteria for enrolment

The following criteria should be checked at the time of study entry. If ANY exclusion criterion applies, the subject must not be included in the study:

- Current alcohol or drug abuse or history of unsuccessfully treated alcohol or drug abuse within the past year
- Unable to perform the study procedures
- Dementia
- Life expectancy less than 1 year
- Any known or suspected immunosuppressive condition, acquired or congenital, as determined by history and/or physical examination (a more detailed description/list can be found in appendix 3).
- Chronic administration (defined as more than 14 continuous days) of immunosuppressants or other immune-modifying drugs within 6 months prior to study participation. The use of topical, inhaled, and nasal glucocorticoids will be permitted (a more detailed description/list can be found in appendix 3).
- Previous participation in this study or in a RSV interventional trial (vaccine, antivirals).
- Planned leave/holiday during the winter season of more than 1 month in total.

4.4 Sample size calculation

For the primary analysis the ratio between cases of RSV-related hospitalizations and number of older adults in the total population will be calculated. In addition, the ratio between the cases of MA-RSV infection and the number of older adults undergoing active surveillance will be calculated.

To estimate the incidence of MA-RSV infection and RSV-related hospitalization at an older age, a prospective cohort of approximately 1,000 older adults ≥60 is followed for 1 year. For sample size calculations a statistic expert of the Julius Support Center was consulted. Assuming a yearly MA-RSV incidence of 3,0% based on literature^{5,9}, a sample size of 800 will produce a two-sided >95% confidence interval with a symmetric half width of 0.01 Version number: 3, July 29th 2019

(Confidence interval formula: Exact, Clopper-Pearson). Accounting for a 10% loss to follow up, approximately 1000 elderly will be included in the cohort.

Patient population	Sites	Outcome	Persons	RSV seasons	Expected Incidence per year (%)	95% Confidence Interval Half-Width (%)
Older Adults (≥ 60 years)	NL, UK, BE	Incidence rate of MA-RSV	1,000	1	3,0 ^{5,9}	1,9 – 5,0

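### Section 4.4 misstates the precision of the MA-RSV incidence estimate: neither the half-width of 0.01 in the text nor the table's 1.9–5.0% is what the named exact method gives

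*Protocol*

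**What the plan says.** Protocol section 4.4 bases the cohort size on the precision of one proportion. The inputs are an expected incidence ("Assuming a yearly MA-RSV incidence of 3,0% based on literature") and a method ("Confidence interval formula: Exact, Clopper-Pearson"). The resulting claim is that "a sample size of 800 will produce a two-sided >95% confidence interval with a symmetric half width of 0.01".

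The step to the enrolment figure is: "Accounting for a 10% loss to follow up, approximately 1000 elderly will be included in the cohort".

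The table that follows lists 1,000 persons, one RSV season and 3.0% expected incidence. Its last column is headed "95% Confidence Interval Half-Width" (in per cent), but the cell holds a lower and an upper limit, 1.9 to 5.0.

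**The concern.** Section 4.4 names every input needed to reproduce its precision figure, and the figure does not come back. The text and the table also describe two different intervals for what should be one design: a half-width of one point around 3.0% is 2.0–4.0%, while the table shows 1.9–5.0%.

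The section contains no hypothesis test, so this precision statement is the only quantitative basis given for the cohort size. A reader cannot tell from it which interval the design is meant to deliver for medically attended RSV. The text is more favourable than the truth and the table less favourable.

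**Working it through.** **Inputs, all from section 4.4:** p = 0.03; n = 800 in the text; n = 1,000 in the table; 10% loss; two-sided 95%; exact Clopper-Pearson.

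**Formula.** For x cases in n people, with α = 0.05:
- lower limit = the α/2 quantile of Beta(x, n − x + 1)
- upper limit = the 1 − α/2 quantile of Beta(x + 1, n − x)
- average half-width = (upper − lower)/2

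**Step 1: the text's figure.** At n = 800, x = 0.03 × 800 = 24.

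| n | x | Exact 95% CI | Lower arm | Upper arm | Average half-width |
|---|---|---|---|---|---|
| 800 | 24 | 1.93%–4.43% | 1.07 | 1.43 | 1.25 points |
| 900 (1,000 less 10%) | 27 | 1.99%–4.33% | 1.01 | 1.33 | 1.17 points |
| 1,000 | 30 | 2.03%–4.26% | 0.97 | 1.26 | 1.11 points |

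Against 1.0 point, the true half-widths are 11% (1.11/1.0) to 25% (1.25/1.0) larger. Put the other way, 1.0 is 10% (1 − 1/1.11) to 20% (1 − 1/1.25) below the true value.

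**Step 2: would another method recover 0.01 at n = 800?**
- Wald: 1.96 × √(0.03 × 0.97/800) = 1.18 points.
- Wilson: 1.20 points.
- Exact Poisson: 1.92%–4.46%, a half-width of (4.46 − 1.92)/2 = 1.27 points.
- Wald at 90% two-sided: n = 1.645² × 0.03 × 0.97/0.01² ≈ 787. This is close to 800 but contradicts the stated confidence level.

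No 95% method tried gives 1.0 point. With the exact method, a half-width of 1.0 point at n = 800 corresponds to about 88% confidence.

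**Step 3: the table cell.** Its half-width is (5.0 − 1.9)/2 = 1.55 points. At exactly 3.0% incidence no sample size gives both limits:
- n = 750 gives 1.90%–4.49%: the lower limit fits, the upper does not.
- n = 450 gives 1.63%–5.03%: the upper limit fits, the lower does not.

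A search over whole case counts finds 1.9–5.0% (to one decimal) only for n between 534 and 594 with 17 to 19 cases, an observed rate of about 3.2%. The lower limit alone agrees with n = 800. The upper limit agrees with none of 800, 900 or 1,000.

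**Step 4: the loss allowance.** 800/0.9 = 889. Going from 800 to 1,000 is an allowance of 1 − 800/1,000 = 20%. A 10% loss from 1,000 leaves 900.

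**The case against.** **Rounding.** The text gives 0.01 to two decimals, and the exact average half-width at 800 is 0.0125, which rounds to 0.01. This may well be how the figure arose, and it is a fair reason not to call it a plain miscalculation. It does not rescue the claim of symmetry. Nor does it reconcile the table, whose half-width of 0.0155 would round to 0.02. One significant digit also covers anything from 0.5 to 1.5 points, which is too coarse around an incidence of 3%.

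**The confidence level.** A reader might take the >95% wording as a further error. It is defensible: Clopper-Pearson coverage is at least nominal, and at n = 800 and p = 0.03 the actual coverage is 96.3%.

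**The loss step.** A reader might infer that the 10% allowance was misapplied and leaves the cohort short. It does not. The protocol says approximately 1,000, and 10% loss leaves 900, more than the 800 planned. The step needs a word of explanation and nothing more.

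**The need for more participants.** An average exact half-width of 1.0 point at 3.0% would take about 1,223 evaluable people. It is tempting to conclude that the cohort is too small. The protocol does not support this: no decision rule or analysis depends on reaching 1.0 point, and a half-width of 1.1–1.25 points is close to what was intended.

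**Harm.** A planning half-width is not a result. The reported interval will come from the observed cases, and section 7 plans descriptive estimation. This stands, and it limits the severity.

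**Conclusion.** The precision statement in section 4.4 is wrong as written. Under its own assumptions (3.0% incidence, exact two-sided 95% interval, observed rate equal to the expected rate), the design gives about 2.0%–4.3% with 900 or 1,000 people and 1.9%–4.4% with 800. The interval is asymmetric at each size. The shortfall against a half-width of 1.0 point is 0.11 to 0.25 points. The table errs in the other direction, with an upper limit of 5.0% where 1,000 persons give about 4.3%, and its heading does not describe its content.

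This is a minor-to-moderate correction of a stated figure. It does not show that the cohort is too small, and it changes neither the conduct nor the analysis of the study.

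**What to change.** Keep the enrolment and reword section 4.4:

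- Replace the precision sentence with: *With approximately 1,000 enrolled and 10% loss (about 900 evaluable), an observed incidence of 3.0% gives an exact two-sided 95% CI of about 2.0%–4.3% (average half-width about 1.2 points, asymmetric).* The reference to a symmetric half-width of 0.01 goes with the old sentence.
- Put the same interval in the table, head the column *95% CI*, and say that it refers to about 900 evaluable people.
- As a clarification, say whether 1,000 is a deliberate rounding up from 889 or reflects a 20% allowance on 800.

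The cost is a protocol wording change. The stated precision becomes slightly less favourable than the present text and more favourable than the present table. No extra participants, visits or analyses are needed.

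### The precision stated in section 4.4 (half-width 0.01 at 3.0% incidence with 800 people) is not reached at 800 or at 1,000, and the table beside it gives a different interval that no sample size produces

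*Protocol*

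**What the plan says.** All the relevant text is in the protocol, section 4.4 (Sample size calculation).

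- The planning incidence: "Assuming a yearly MA-RSV incidence of 3,0% based on literature".
- The precision claim: "a sample size of 800 will produce a two-sided >95% confidence interval with a symmetric half width of 0.01".
- The method: "Confidence interval formula: Exact, Clopper-Pearson".
- The step to the enrolled number: "Accounting for a 10% loss to follow up, approximately 1000 elderly will be included in the cohort".
- The table has one row, for older adults: 1,000 persons, one RSV season, expected incidence 3.0%. Its last column is headed "95% Confidence Interval Half-Width" (in per cent), and the entry is the range 1.9 to 5.0.

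**The concern.** Section 4.4 describes the precision of the primary incidence estimate twice, and the two descriptions disagree. A symmetric half-width of 0.01 around 3.0% means 2.0% to 4.0%. The table gives 1.9% to 5.0%, whose average half-width is (5.0 − 1.9)/2 = 1.55 points, under a heading that announces a half-width rather than limits.

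The text also looks wrong on its own terms. A Clopper-Pearson interval around a small proportion is not symmetric, and 800 people appear too few for ±1 point at 3%.

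The study is descriptive (section 7) and its primary endpoint is an incidence rate (section 5.1.1). The expected interval width is therefore the only quantitative reason given for the cohort's size. If it is misstated, a reader cannot tell how precisely the main result was meant to be known.

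**Working it through.** **Inputs, all from section 4.4.** Incidence p = 0.03; n = 800 for the precision claim; about 1,000 enrolled; 10% loss; two-sided 95%; Clopper-Pearson. Taking 10% off 1,000 leaves 900 evaluable.

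**Formulas.** With x = 0.03n cases:

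- lower limit = the 0.025 quantile of Beta(x, n − x + 1)
- upper limit = the 0.975 quantile of Beta(x + 1, n − x)
- average half-width = (upper − lower)/2
- simple normal (Wald) half-width, for comparison = 1.96 × √(0.03 × 0.97/n)

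**Step 1: the plan's figure at n = 800.** With x = 24 the limits are 1.93% and 4.43%. The arms are 3.00 − 1.93 = 1.07 and 4.43 − 3.00 = 1.43 points, and the average half-width is (4.43 − 1.93)/2 = 1.25 points. The stated 1.00 is not reproduced, and the interval is not symmetric. The Wald interval is symmetric, but its half-width is 1.18 points.

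**Step 2: other sizes the plan could mean.**

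| n | Cases at 3.0% | Exact 95% interval (%) | Arms (points) | Average half-width | Wald half-width |
|---|---|---|---|---|---|
| 800 | 24 | 1.93 to 4.43 | −1.07 / +1.43 | 1.25 | 1.18 |
| 900 | 27 | 1.99 to 4.33 | −1.01 / +1.33 | 1.17 | 1.11 |
| 1,000 | 30 | 2.03 to 4.26 | −0.97 / +1.26 | 1.11 | 1.06 |

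No row reaches 1.00 by either method. At n = 889, which is 800/0.9, the exact average half-width is 1.18 points.

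**Step 3: what a half-width of 0.01 would take at 3.0%.** An average Clopper-Pearson half-width of at most 1.00 point first occurs at n = 1,223 evaluable. If the longer, upper arm must also be within 1.00, n = 1,484. Wald needs 1,118. Looked at the other way, the exact interval for 24/800 has a total width of 2.00 points only at a confidence level of 87.9%. A 90% Wald interval gives ±1.00 at n = 788, close to 800. That may be where the 800 came from, but the protocol does not say so.

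**Step 4: the table entry.** For the row's own inputs (1,000 persons, 3.0%) the exact interval is 2.03% to 4.26%, not 1.9% to 5.0%. At 3.0%:

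- a lower limit that rounds to 1.9% needs n between 678 and 832;
- an upper limit that rounds to 5.0% needs n between 443 and 479.

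The ranges do not overlap, so no n gives the entry. A search over whole-number counts for n from 200 to 2,000 finds limits rounding to 1.9 and 5.0 only for n between 534 and 594, with 17 to 19 cases and an observed incidence of 3.16% to 3.22%.

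**The case against.** The arithmetic is hard to dispute. The case on the other side is about how much it matters and how it should be described.

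- *Rounding.* At two decimals 0.0125 and 0.0111 both print as 0.01. This does not rescue the claim. The same rounding would hold from n = 568, so it cannot justify choosing 800, and it explains neither the symmetry nor the table.
- *Direction.* Only the text promises too much. The table errs the other way: 1.9 to 5.0 contains the true interval at 800, 900 and 1,000. This stands, and the fault is best described as two wrong and conflicting statements.
- *The phrase about more than 95%.* Clopper-Pearson intervals are conservative. At a true incidence of 3.0% the actual coverage is about 96.3% at n = 800 and 95.9% at n = 1,000, so the phrase can be defended as a statement about coverage. This stands too. Replacing it with the plain term, exact 95% interval, is for clarity.
- *Consequence.* The shortfall is a fraction of a percentage point, no test or power claim depends on it, and the reported interval will be computed from the observed cases. The primary result will not be biased. This limits the consequence but does not make the stated figures right.
- *Choice of N.* The protocol never states 900. It follows from 1,000 less 10%, while the text names 800. The sponsor does need to say which evaluable number is meant.

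**Conclusion.** The concern holds. At 3.0% incidence and with the method the protocol names, the average half-width is 1.25 points at 800 (25% above the stated 1.00), 1.17 at 900 and 1.11 at 1,000 (11% above). The upper limit at 800 is 4.4%, where the text implies 4.0%. The table's 1.9 to 5.0 is a separate error in the opposite direction: too wide for its own row, unattainable at 3.0%, and filed under the wrong heading.

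This rests on the protocol's own inputs and on reading the half-width as half the total interval width, the most favourable reading for an asymmetric interval. Judged by the longer arm, the gap is larger (1.43 points at 800). The error affects the stated planning precision only. It should still be corrected, because nothing else in the document justifies the sample size.

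**What to change.** Keep the enrolment and restate the figures in section 4.4.

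1. Declare the evaluable number. If it is 1,000 less 10%, a suitable sentence is: *With 900 evaluable participants and a 3.0% incidence (27 cases), the exact (Clopper-Pearson) 95% confidence interval is 2.0% to 4.3%.* If 800 is the intended number (24 cases), the interval is 1.9% to 4.4%.
2. Remove the claim of a symmetric half-width of 0.01, and write exact 95% interval in place of the more-than-95% wording.
3. In the table, rename the last column 95% CI (%), replace 1.9 to 5.0 with the interval for the evaluable number, and show that number in the row. If the row keeps 1,000 as the analysed number, the entry is 2.0 to 4.3.

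The cost is one sentence and one table column. The stated precision becomes slightly less favourable than the text now claims, and no further participants are needed. If ±1.0 point is a real requirement, about 1,223 evaluable people would be needed, or about 1,359 enrolled at 10% loss (1,223/0.9), and the sponsor should say so explicitly.

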5. METHODS

5.1 Study parameters/endpoints (see also Table 1)

5.1.1 Main study parameter/endpoint

The primary endpoint is the incidence rate of RT-PCR confirmed medically attended RSV infection-associated ARTI in both inpatients and outpatients as well as the incidence of RSV in the overall study population of older patients. The incidence rate will also be summarized separately for outpatient events and for both inpatient and outpatient events combined through the RSV season of follow up. Nasopharyngeal and oropharyngeal swabs collected during ARTI episodes during the RSV season will be used for reverse transcriptase polymerase chain reaction (RT-PCR) detection of RSV. Pre- and post RSV-season RSV serology will be performed in order to capture RSV infected individuals which will be missed by active surveillance. In order to analyze the microbiome and transcriptome a nasopharyngeal and oropharyngeal swab will be collected pre- and post RSV-season.

5.1.2 Secondary study parameters/endpoints

- The incidence rate of all-cause MA-ARTI or events leading to worsening of cardiorespiratory status. The incidence rate will also be summarized separately for outpatient events and for both inpatient and outpatient events combined through the RSV season of follow up. Subgroup analyses will summarize these endpoints by RSV season.
- 2. Mortality through the RSV season of follow up for RSV-associated deaths and all cause deaths.
- 3. Health care costs and resource use for RSV-associated and all-cause MA-ARTI (inpatient or outpatient) or events leading to worsening cardiorespiratory status with regard to hospital duration, incidence and duration of intensive care unit stay, supplemental oxygen use, antibiotic and antiviral use and number of outpatient visits (e.g., ER visit, physician office/outpatient visits) and HRQoL.
- The incidence rate of RSV-associated secondary bacterial pneumonia events (defined as pneumonia within 21 days after RSV infection) and associated antibiotic use will be summarized.
- 5. Change in frailty over the course of study.
- 6. Sample collection for biomarker analysis to investigate possible biomarkers which are predictive of severe or complicated RSV disease in older adults. With these

clinical samples a biobank will be established for identifying potential biomarkers of RSV disease severity for further validation.

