2. OBJECTIVES

 Table 1. Primary and secondary objectives and associated endpoints.

	Objectives	Endpoints
Primary	To estimate the incidence of RSV MA-ARTI in both inpatients and outpatients and overall RSV infection-associated ARTI in older adults.	Incidence rate of RT-PCR confirmed RSV infection-associated MA-ARTI in inpatients outpatients and overall RT-PCR confirmed RSV in older adults. Data collected by using samples, medical data from the hospital and questionnaires.
Secondary	To estimate the rate of all-cause MA (inpatient or outpatient) ARTI and related medical complications (exacerbations of chronic conditions, acute cardiovascular events).	Incidence rate of all-cause MA ARTI or events leading to worsening of cardiorespiratory status. Data collected by using diary, questionnaires.
	To estimate the RSV- associated and all-cause mortality.	 Mortality through the RSV season of follow up for RSV- associated deaths and all cause deaths. Data collected by using medical data from the hospital and questionnaires.
	To estimate health care costs, health care resource use, interruption of normal activities, and HRQoL in RSV-associated and all-cause MA (inpatient or outpatient) ARTI patients.	Health care costs and resource use, interruption of normal activities, and HRQoL in RSV-associated and all-cause MA (inpatient or outpatient) ARTI patients. Data collected by using diary, questionnaires.
	To estimate the incidence of RSV-related secondary bacterial pneumonia events and their association with antibiotic use within 21 days after onset of RSV infection.	Incidence rate of RSV- associated secondary bacterial pneumonia events (defined as pneumonia within 21 days after RSV infection) and associated antibiotic use. Data collected by using medical data from the hospital, diary and questionnaires.
	 To collect clinical samples for biomarker analysis on possible biomarkers which are predictive of 	Sample collection for biomarker analysis. Establish a Biobank for identifying potential biomarkers of

severe or complicated RSV disease in older adults. With these clinical samples a biobank will be established for identifying potential biomarkers of RSV disease severity for further validation.	RSV disease severity for further validation.
To examine the incidence of other respiratory pathogens associated with all MA-ARTI	 Incidence rate of other respiratory pathogens associated with all MA-ARTI. Data collected by using samples.

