5.3 Study procedures

1. Inclusion Visit (August/September)

At the inclusion visit, after eligibility has been confirmed and fully informed consent completed, the following procedures will take place:

- A baseline questionnaire about, but not limited to, demographic data, medical history, risk factors for RSV disease and quality of life will be completed.
- A blood sample (60 ml) and a nasopharyngeal sample will be collected.
- 2. Throughout the RSV season (October 1st to May 1st, or longer if RSV is still circulating based on national viral surveillance programs):

Participants will be asked about respiratory symptoms during the RSV winter season by weekly contact by telephone (verbally or text message), email, telephone app or online questionnaire. If they experience an ARTI, participants are instructed to contact the study team. Two nasopharyngeal and one oropharyngeal sample will be collected by home visits (or in the doctor's office when preferred by participant) within 3 days after contact with the study team. One nasopharyngeal sample will be used for direct RSV RT-PCR testing. The other samples will be stored at -80°C. If RSV is positive a blood sample will be drawn (60 ml) and a nasopharyngeal sample will be collected and stored at -80°C. In addition, in case of a RSV ARTI, 1-2 weeks after onset of symptoms another blood sample (30ml) and nasopharyngeal sample will be collected. During the episode of respiratory disease, participants are asked to complete a diary on respiratory symptoms and HRQoL. At the end of the episode, participants are asked to complete a questionnaire on medical resource use, interruption of daily activities and HRQoL. If participants have been admitted to the hospital, a questionnaire about the reason for hospitalization, diagnosis and treatment will be completed by the study team using medical data from the admitted hospital.

- 3. At the end of the RSV Season (May/June)
 - A blood sample (60 ml) and a nasopharyngeal sample will be collected.
- 4. Approximately one year after inclusion (+/- 2 months).
 - A questionnaire about changes in living conditions, health status and quality of life will be completed.

 Table 2. Overview of sampling of older adults study.

Moment of	Sample	Volume	Analysis (minimum
sampling		00 1	amount)
At beginning of RSV	Serum (venous)	20 ml	RSV serology (350-400 μl)
season (Oct.)			Proteome (100 µl)*
	Paxgene (venous)	10 ml	Transcriptome (200 µI)*
	Whole blood	30 ml	DNA/GWAS (200 µl)

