	(venous)		Epigenetics*
			Cellular immunology#
	Nasopharyngeal	n/a	Airway microbiome
	swab		Airway transcriptome*
ARTI	Nasopharyngeal	n/a	RSV RT-PCR (qualitative)
	swab (2x) and		Multiplex RT-PCR
	oropharyngeal swab		respiratory viruses
			(quantitative) (pending
			funding)
			(RSV viral (deep)
			sequence analysis)
RSV ARTI	Serum (venous)	20 ml	RSV serology (350-400 µl)
			Proteome (100 µl)*
	Paxgene (venous)	10 ml	Transcriptome (200 µI)*
	Whole blood	30 ml	Epigenetics*
	(venous)		Cellular immunology#
	Nasopharyngeal	n/a	Airway microbiome
	swab		Airway transcriptome*
1-2 weeks after RSV	Nasopharyngeal	n/a	Airway microbiome*
ARTI	swab	11/4	All way microbiome
74(11	Whole blood	30 ml	Cellular immunology#
	(venous)	00 1111	Condidi mimanology
At end of RSV	Serum (venous)	20 ml	RSV serology (350-400 µl)
season (May)			Proteome (100 µl)*
	Paxgene (venous)	10 ml	Transcriptome*
	Whole blood	30 ml	Epigenetics*
	(venous)		
	Nasopharyngeal		Airway microbiome
	swab		Airway transcriptome*

^{*} and additional RSV related biomarkers

[#]in subset of subjects

Handling and storage of samples

All samples will be stored at the site where they are collected (medical center or local laboratory):

- Blood samples will be collected in appropriate tubes as described in table 2 and will be stored at -80°C for later analysis.
- Nasopharyngeal swab: a nasopharyngeal swab will be collected and aliquoted directly in 3-4 samples of 200 microliter. All aliquots will be stored at -80°C for later analysis
- Oropharyngeal swab: an oropharyngeal swab will be collected and stored at -80°C for later analysis.

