8.2 Recruitment and consent

General practice patient lists will be screened for potentially eligible participants (see section 4.2 and 4.3). The latter will be informed by their GP about the study. If they are interested in taking part their contact details will be given to the study team. Interested potential participants will be contacted by a member of the study team who will answer any questions they may have about the study and if they are still interested booked in for an inclusion visit. Recruitment procedures can be adapted to local circumstances and regulations.

Participants that report a pneumonia during the study, or have missing data concerning a medically-attended ARTI, are asked additional informed consent to perform a medical notes review. This notes review includes amongst others obtaining report of physical examination, performed scans (chest X-ray), blood testing (CRP/ESR), prescription of medication (such as antibiotics or respiratory medication) and clinical diagnoses made by the physician. A medical notes review will be performed only in these specific cases in order to obtain or validate this information which is key for the primary and secondary study outcomes.

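### The secondary bacterial pneumonia endpoint has no bacterial criterion, so it counts primary RSV pneumonia and is at best an upper bound

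*Protocol*

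**What the plan says.** The objective in Table 1 (protocol section 2) reads: "To estimate the incidence of RSV-related secondary bacterial pneumonia events and their association with antibiotic use within 21 days after onset of RSV infection". The endpoint set against it in the same table is "defined as pneumonia within 21 days after RSV infection) and associated antibiotic use". Section 5.1.2 repeats that definition: "The incidence rate of RSV-associated secondary bacterial pneumonia events (defined as pneumonia within 21 days after RSV infection". It says that the incidence rate and the associated antibiotic use will be summarised.

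Two other parts of the protocol bear on how a pneumonia could be classified. Section 5.3 describes what is tested when a participant has an ARTI, and provides for a questionnaire on diagnosis and treatment, completed from hospital data, for anyone admitted. Section 8.2 provides for a medical notes review when a participant reports a pneumonia, subject to additional consent. The review covers, among other items, "performed scans (chest X-ray), blood testing (CRP/ESR", prescriptions and the physician's diagnoses.

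**The concern.** The endpoint's name makes two claims about each event: that the pneumonia is bacterial, and that it is secondary to the RSV illness. The definition tests neither. It has an upper time limit but no stated lower one, no requirement that the patient improve and then worsen, and no exclusion of RSV pneumonia. A pneumonia caused by RSV a few days into the illness meets it.

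The study would then report, as the incidence of bacterial complications of RSV, a count that mixes viral and bacterial pneumonia. The antibiotic use summarised alongside has the same problem: prescribing for viral pneumonia cannot be told apart from treatment of a bacterial complication. A reader who takes the label at face value would overestimate how often RSV in older adults leads to bacterial pneumonia.

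**Working it through.** The protocol states no expected figure for this endpoint, so there is none to reproduce. The check sets the passages side by side and then shows what the definition implies arithmetically.

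**Step 1: objective against definition.** The objective (Table 1) asks for secondary bacterial pneumonia. The operative definition, in Table 1 and in section 5.1.2, is "pneumonia within 21 days after RSV infection". The same words appear in both places, so this is not a slip in one of them.

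**Step 2: does another section supply the missing criterion?**

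- *Section 5.3, ARTI sampling.* "One nasopharyngeal sample will be used for direct RSV RT-PCR testing. The other samples will be stored at -80°C". Table 2 lists RSV RT-PCR, a respiratory virus multiplex that depends on funding, and viral sequencing for ARTI samples. For RSV ARTI it adds serology, proteome, transcriptome, epigenetics and cellular immunology. The only entry that touches bacteria is "Airway microbiome", and nothing links it to the pneumonia endpoint. No diagnostic bacteriology is listed.
- *Section 7.* It gives descriptive statistics and group comparisons, but no case rule.
- *Appendix 2.* The glossary defines ARTI but not pneumonia.
- *Section 8.2, notes review.* It collects relevant clinical data but names no culture or antigen test. It requires extra consent and gives no rule for turning its content into a bacterial classification.
- *Section 5.3, hospital questionnaire.* It records the diagnosis for admitted participants, again without a classification rule.

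No section supplies the criterion.

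**Step 3: what the definition does to the rate.** Let N be the pneumonias counted and q the share that are truly secondary bacterial. The reported rate is proportional to N and the rate the objective asks for is proportional to qN, so

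reported / intended = N / (qN) = 1/q.

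The protocol gives no value for q. As an illustration with assumed values:

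| Assumed q | Factor 1/q |
|---|---|
| 25% | 4.0 |
| 50% | 2.0 |
| 75% | 1.33 |

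The factor is 1 only if every pneumonia in the window is secondary bacterial.

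**Step 4: how many events are at issue.** Section 4.4 assumes a yearly medically attended RSV incidence of 3.0% in about 1,000 people: 0.03 × 1,000 = 30 cases. If 5% to 30% of these had pneumonia in the window (assumption; the protocol gives no figure), the count would be 30 × 0.05 = 1.5 to 30 × 0.30 = 9. The exact (Clopper-Pearson) 95% interval is 0.6 to 8.7 per 1,000 for 3 events in 1,000, and 4.1 to 17.0 per 1,000 for 9 events. With so few events, the cause of two or three pneumonias decides most of the estimate.

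**The case against.** The strongest reply is that the parenthesis fixes only the time relation to RSV, that the word bacterial in the endpoint's name still has force, and that the notes review and hospital data exist to apply it. Section 8.2 does say that the review serves to obtain or validate information key to the primary and secondary outcomes. This stands in part: relevant data are planned, and the protocol is better placed than the definition alone suggests. But the text says that the event is *defined as* pneumonia in the window, and no section says how the data would separate bacterial from viral cases. An analysis plan could add criteria, but it would then depart from an explicit protocol definition rather than fill a gap.

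Four stronger readings are tempting, and the protocol does not support them.

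- *The endpoint is useless.* It is not. It measures RSV-associated pneumonia of any cause, which is informative and bounds the bacterial rate from above if ascertainment is complete.
- *The antibiotic analysis is circular.* Only the objective in Table 1 speaks of an association; section 5.1.2 promises a summary. The fair complaint is that the summary mixes viral and bacterial cases.
- *The 21-day windows conflict.* In the objective, "association with antibiotic use within 21 days after onset of RSV infection" can be read as a limit on antibiotic use, not as a competing window for pneumonia. The two endpoint texts agree with each other.
- *The published rate must come out too high overall.* Mislabelling pushes it up, but pneumonias not reported or RSV infections not swabbed would push it down. The protocol does not allow the two to be netted.

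It is also fair to say that this is one descriptive secondary endpoint with few expected events. Imprecision limits the practical consequence but does not make the label correct.

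**Conclusion.** The point holds. The protocol fixes an explicit definition that does not match its objective: primary RSV pneumonia within 21 days counts as a secondary bacterial event. The reported rate is at best an upper bound for secondary bacterial pneumonia, and the antibiotic use reported with it includes use for viral pneumonia.

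The overstatement from mislabelling is 1/q for an unknown q, and no multiple should be quoted as a property of this study. The conclusion rests on the literal wording of Table 1 and section 5.1.2 and on the absence of a classification rule elsewhere in the protocol. It does not rest on any assumed q. An analysis plan, if there is one, was not available. The change should be made, but it concerns a secondary endpoint and does not affect the primary incidence estimates.

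**What to change.** In Table 1 and section 5.1.2, rename the endpoint *RSV-associated pneumonia (any cause) within 21 days after onset of RSV ARTI symptoms*. This says what is measured and ties the window to a date that can be recorded. Summarise antibiotic use for this endpoint under the same name.

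Report *probable secondary bacterial pneumonia* only as a prespecified subset, classified from data already planned: chest X-ray, CRP/ESR, physician's diagnosis and timing after onset from the notes review, and hospital diagnosis for admitted participants. Write the classification rule before the data are reviewed. Show cases without consent or without sufficient data separately as unclassifiable, not as non-bacterial. Align the wording of the objective in Table 1.

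The cost is protocol and analysis plan wording plus the work of applying the rule to a handful of cases; no new sampling is needed. The limitation is that the subset will be small, incomplete because it depends on extra consent, and without microbiological confirmation. The report should say so.
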